9.1. Additional Efficacy Analysis

Additional efficacy parameters include the duration of response (DOR), the injected tumor response (ITR), the bystander tumor response (BTR), progression free survival (PFS), and overall survival (OS). These endpoints will be summarized by treatment (see section 7 for definition of each treatment) and subgroup. Other than 1 listing reporting bystander tumors' diameter that declined over time that declined (noted below), the bystander tumor response rate (BTR) analysis will be conducted separately from the SAP from collected radiographic data.

DOR is defined as the time from first tumor assessment of CR, PR, or SD to the time of progressive disease or death due to any cause. For responders with no death or progression, DOR will be censored on the last non-PD tumor assessment or follow-up call.

The median DOR as obtained from Kaplan-Meier methods will be presented by treatment and subgroup and will include the median, 25th percentile, 75th percentile, and a 2-sided point-wise 95% confidence interval.

ITR will be based on the target tumors at the baseline visit; tumors that become target during the study will also be included in the ITR calculation at the time they are treated. The ITR is defined as the ratio of CR + PR in injected tumors / total number of injected tumors. Thus, bystander or non-target lesions dosed at later dates are not included in calculations for ITR.

The ITR will be calculated based on the maximum likelihood estimator and summarized in tables. The estimate of ITR will be accompanied by 2-sided 95% exact binomial confidence intervals as determined by the Clopper-Pearson method and assessed at each study-specified timepoint where an assessment is performed.

The BTR will follow the same definition as the ITR for bystander tumors. Note that bystander tumors that are injected on study will be included in the ITR calculation.

Individual tumor assessments for target and bystander, non-target, and new lesions will be listed, with location, method of assessment, longest diameter, shortest diameter, depth, volume, and percent change from baseline included for each target and bystander tumor, as well as Total Tumor Burden at Baseline, Cumulative Dose, Percent TTB dosed, and dose category (< 40% versus \geq 40%) per subject. Another listing will be produced for the Abscopal effect of bystander tumors, defined as any bystander tumor with any decrease in tumor size at any point during the study, but before being injected with study drug.

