For DCR, exact binomial 95% confidence intervals will be determined by Clopper-Pearson method. Median time to response and duration of response will be summarized for those subjects with confirmed responses, using Kaplan-Meier method; Progression free survival (PFS) will be similarly summarized. Individual tumor measurements, tumor burden and % changes in tumor burden will be listed. Changes in tumor burden will be presented graphically.

14.3.4. **Concomitant Medication**

Concomitant medications will be coded using the World Health Organization Drug Dictionary (WHODD). Concomitant medications will be summarized. Tabulation will be made with respect to the proportion of subjects taking at least 1 concomitant medication for each preferred term during the study. A listing of concomitant medications by subject will be provided.

14.3.5. **Safety**

The primary objective is to assess the safety and tolerability of multiple intratumoral doses of INT230-6 in subjects with advanced or recurrent malignancies. This will be assessed by the rate of \geq grade 3 AEs

Protocol IT-01 Version Amendment 6

attributed to study drugs (INT230-6 and others per the appropriate protocol supplement), and study procedure, and not the underlying disease.

Safety Analyses:

All recorded adverse events will be listed and tabulated by system organ class, preferred term, and coded according to version 19.1 of Medical Dictionary for Regulatory Activities (MedDRA). The incidence of adverse events will be tabulated and reviewed for potential significance and clinical importance. Vital signs and clinical laboratory test results will be listed and summarized. Any significant physical examination (PE) findings and results of clinical laboratory tests will be listed. Electrocardiogram (ECG) listings will be evaluated by the investigator and abnormalities, if present, will be listed.

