18.1.4. Response and Stable Disease Duration (RECIST 1.1 and iRECIST)

Response duration will be measured from the time measurement criteria for CR/PR or iCR/iPR (whichever is first recorded) are first met until the first date that recurrent or progressive disease is objectively documented, taking as reference the smallest measurements recorded on study (including baseline).

Stable disease duration will be measured from the time of start of treatment until the criteria for progression are met, taking as reference the smallest sum on study (including baseline).

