9.2. Progression-Free Survival and Overall Survival

Progression free survival (PFS) and Overall Survival (OS) will be evaluated for the All Treated Population, the REP, and the SEP. PFS will be defined as the time (in months) from first dose of INT230-6 to either observation of clinical deterioration, removal from study, or occurrence of death due to any cause within 126 days (approximately 2 time intervals for tumor assessments) of the last tumor assessment. Progression date will be defined as the end of treatment date as captured per eCRF guidelines when the reason for end of treatment is either 'Radiographic

deterioration' or 'Clinical deterioration.' In subjects without a progression date or with a death date more than 126 days after the last tumor assessment, the PFS time will be censored on the date of last tumor assessment or last treatment date if the subject has no post-baseline tumor assessments. PFS analyses will consider tumor assessments after treatment discontinuation.

OS will be defined as the time (in months) from first dose of INT230-6 to death. Subjects for whom death is not reported will be censored at the date of end of study.

PFS and OS will be summarized in a listing. The median time to OS as obtained from Kaplan-Meier methods will be tabulated by subgroup and will include the median, 25th percentile, 75th percentile, and a 2-sided point-wise 95% confidence interval. Hazard ratios may be determined between certain curves for the Kaplan Meier figures noted below.

A Kaplan Meier figure of OS for the All Treated, REP, and SEP populations will be presented for each of the following:

- a curve all treated monotherapy patients, a curve for subjects that received a dose to total tumor burden < 40% of tumor burden, a curve for those subjects that had a dose to total tumor burden \geq 40%,
- a curve for escalation cohort combining A1, B1, EA, EC, and a curve for escalation cohort combining EC2 and EC3,
- a curve for sarcoma patients in the monotherapy cohort and a curve for monotherapy sarcoma patients having \geq 40% of their total tumor burden treated,
- a curve for the pembrolizumab DEC/DEC2 combined cohort for subjects,
- a curve for all ipilimumab FEC cohort subjects,
- a curve for the ipilimumab FEC sarcoma subjects, a curve for all monotherapy sarcoma patients and a curve for monotherapy sarcoma subjects having \geq 40% of their total tumor burden treated will be included.

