13. CHANGES IN THE STATISTICAL METHODS FROM THOSE STATED IN THE PROTOCOL

None.

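### SAP 9.1 starts duration of response at the first CR, PR or SD, the protocol starts it at CR/PR, and SAP 13 declares no change

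*SAP*

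**What the plan says.** **SAP.** Section 9.1 reads: "DOR is defined as the time from first tumor assessment of CR, PR, or SD to the time of progressive disease". Death from any cause is the other end event. The next sentence is "For responders with no death or progression, DOR will be censored on the last non-PD tumor assessment or follow-up call". Section 9.1 then asks for a Kaplan-Meier median, quartiles and a 95% confidence interval by treatment and subgroup. The SAP synopsis limits the duration-of-response summary to subjects who had a response and says nothing about confirmation. Section 13, headed "CHANGES IN THE STATISTICAL METHODS FROM THOSE STATED IN THE PROTOCOL", has the single entry None.

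**Protocol.** Section 18.1.4, whose heading covers both RECIST 1.1 and iRECIST, keeps two quantities apart. The first is "Response duration will be measured from the time measurement criteria for CR/PR or iCR/iPR". The second is "Stable disease duration will be measured from the time of start of treatment until the criteria for progression are met". On who is analysed, section 14.3.3 says "Median time to response and duration of response will be summarized for those subjects with confirmed responses", and the protocol synopsis says the same.

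**The concern.** A duration of response should measure how long a subject stays in CR or PR. SAP 9.1 lets an SD assessment start the clock, so it merges two quantities that the protocol defines separately and starts at different points. It also does not carry over the confirmation condition. None of this is declared.

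Two things are at stake. A responder who passed through SD is credited with time before any response existed. And the wording leaves room for two programmers to build two different analysis sets, one of CR/PR subjects and one that also holds SD-only subjects. The resulting median would be tabulated under the name duration of response either way.

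**Working it through.** The documents give no expected median or sample size for this endpoint, so there is no planned figure to reproduce. The check compares the definitions and then sizes the start-date shift.

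**1. When the clock starts**

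| Source | Start of response duration | Treatment of SD |
|---|---|---|
| Protocol 18.1.4 | CR/PR or iCR/iPR criteria first met | Separate duration, from start of treatment |
| SAP 9.1 | First CR, PR or SD | Starts the same clock |

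**2. Who enters**

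- Protocol 14.3.3 and protocol synopsis: confirmed responders. Protocol 12.2.2 builds the overall response rate on confirmed CR or PR, so SD is not a response there.
- SAP synopsis: subjects with a response, confirmation not mentioned.
- SAP 9.1: the definition names SD, while the censoring sentence speaks of responders.
- The SAP synopsis and the word responders point towards a CR/PR-only set. They do not settle it, because the SAP synopsis, in defining the disease control rate, also calls stable disease a response.

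**3. Shift for a responder first rated SD (applies whoever else enters)**

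Inputs: first scan at 12 weeks, then every 9 weeks, each with a window of 10 days either side (SAP 4.4; footnote 10 to protocol Tables 11 to 13).

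- Nominal shift per interval between first SD and first CR/PR: 9 × 7 = 63 days, or 63 / 30.4375 = 2.07 months.
- With windows: 63 − 20 = 43 days to 63 + 20 = 83 days.
- Two or three intervals: 18 or 27 weeks.
- Example: SD at week 12, PR at week 21, progression at week 39. SAP: 39 − 12 = 27 weeks. Protocol: 39 − 21 = 18 weeks.
- Other schedules give another step. The 8-week follow-up in protocol 5.3 (before Amendment 6) and SAP 4.1.4 gives 8 × 7 = 56 days. Protocol 12.1.3.1 gives assessments every 2 months and later every 3 months for A1 and B1.

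In a CR/PR-only set the median does not move if no responder was first rated SD. It moves by 63 days if every responder was, each by one nominal interval. The documents do not give that share.

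**4. If SD-only subjects enter**

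Their SAP duration matches neither protocol quantity. It is not a response duration, and it starts at the first SD assessment rather than at start of treatment: 12 × 7 = 84 days later if SD is first recorded at the first scheduled scan. Earlier starts for responders lengthen times, while SD-only subjects may progress sooner or later than responders. The pooled median can therefore go up or down. Sizing it would need the SD and CR/PR rates and both time distributions, none of which is given. The illustrated counts of 3 to 5 out of 16 do not help: SAP 5 and protocol 14.1 attach them to objective response, and the protocol synopsis attaches the same counts to disease control.

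**5. End rules, as a consistency check only**

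Duration of response counts death at any time and may be censored at a follow-up call. Under SAP 9.2, PFS counts death only within 126 days of the last tumor assessment; otherwise "the PFS time will be censored on the date of last tumor assessment or last treatment date". Example: PR at week 21, last scan at week 30, no progression or removal from study recorded, death at week 60. The gap is (60 − 30) × 7 = 210 days, more than 126, so PFS is censored at 30 weeks. Duration of response from PR is an event at 60 − 21 = 39 weeks, longer than the same subject's PFS. This needs scheduled scans after week 30 not to have been done.

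**The case against.** **The SAP openly modifies the criteria.** SAP 9 does explain that CR, PR, SD and progression are rated by modified rules. That concerns how an assessment is rated. It does not mention the start of response duration or confirmation, and SAP 13 still says None.

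**The analysis set is probably CR/PR only.** This has force, and it removes the mixing problem if it is what was meant. It does not remove the start-date problem: a responder first rated SD still starts at SD.

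**Confirmation is not clearly required.** This stands in part. Protocol 14.3.3 says confirmed, but 18.1.4 dates response from when criteria are first met, and a note to protocol Table 16 assumes that confirmation is not needed. That note is framed for a randomised study, which this is not, so it does not cancel 14.3.3. A reader might infer that the SAP plainly breaks a settled confirmation rule; the protocol is not consistent enough to support that.

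**The end rules can be defended.** This largely stands. SAP Appendix 1 item 5 lets progression be captured on follow-up and survival forms, so censoring at a follow-up contact can be coherent. A reader might infer that duration of response should be censored at the last scan. If later events still counted, that would end event-free follow-up early and could bias the duration downward. The protocol gives no censoring rule for this endpoint, so there is no departure here.

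**The endpoint is minor.** It is exploratory in SAP Table 2, untested and unpowered, and protocol sections 4.2 to 4.4 do not name it. This limits the severity. It does not make the definition right.

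**Conclusion.** The point holds, at the level of something that should be fixed. As written, SAP 9.1 departs from protocol 18.1.4 on the start of response duration, and the departure is undeclared. The certain effect is on responders first rated SD: about 63 days too long per scan interval (43 to 83), assuming the 12-week then 9-week schedule, and a different amount in cohorts on other schedules.

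A reader might go further and infer that SD-only subjects certainly enter, or that the reported median is inflated or deflated by a stated amount. The documents do not support either. The set is ambiguous, with the balance of wording towards CR/PR only, and any median for a mixed set would rest on rates and durations that neither document supplies. If SD-only subjects do enter, all that can be said is that the figure is a duration of disease control and that its direction of change is unknown. Nothing here affects the primary safety objective or the disease control rate.

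**What to change.** 1. In SAP 9.1, start duration of response at the first assessment of CR or PR, include only subjects with CR or PR, and make 9.1 and the SAP synopsis agree.
2. Either apply the confirmation requirement of protocol 14.3.3 or declare that it is dropped, and say how the note to protocol Table 16 is to be read.
3. If a duration that includes SD is wanted, report it separately as duration of disease control, or report SD duration from first dose in line with protocol 18.1.4.
4. Enter any departure that is kept in SAP 13.
5. For consistency, reconcile the end rules for duration of response and PFS (late deaths, follow-up-call censoring) with each other and with the progression definition in SAP Appendix 1 item 5. This need not mean censoring at the last scan.

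The cost is SAP wording and one derivation rule that uses assessment dates already recorded. The downside is a smaller analysis set and a wider interval, to the extent that SD-only or unconfirmed subjects would otherwise have entered.

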12.1.4. Follow-up Period

Follow-up visits will be conducted after completion of the Treatment Period (induction and maintenance for those cohorts with maintenance treatment) or as indicated in Section 5.4. Patients who receive all 5 treatment doses or discontinue treatment for any reason except Disease Progression, or Withdrawal of consent should enter Long Term Follow up Period. These patients are to be evaluated every 9 weeks including scans until disease progression or they receive an intervening anti-cancer medication. After documented disease progression or receipt of an intervening anti-cancer medication, patients will enter Survival Follow up. During this time, patients will be contacted every 3 months for patient status (phone call or clinic visit). For subjects who discontinue treatment due to progression, follow-up should be completed approximately every 3 months as noted below (survival follow up). Completion of subsequent follow-up visits will depend on the status of the subject at the end of treatment. All subjects will be followed from the last visit until progression, initiation of a new therapy, or the duration of the study (4 years), whichever occurs first.

Following completion of the treatment and follow-up periods, all subjects will be followed for survival after completion of treatment phases and through the follow up period of the protocol. Subjects will have their survival status assessed approximately every 3 months by either a telephone, in-person contact, or chart review until study completion or termination by the Sponsor. No other data (e.g., subsequent therapies, performance status etc.) beyond survival will be collected during these calls/visits.

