4.1.4. Long Term Follow up

Subjects who complete a full course of treatment including those who receive retreatment or who have discontinued treatment for any reason other than clinical or radiological progression will enter the Long Term Follow up period. During this time, subjects will be evaluated every 8 weeks for the first year and every 3 months thereafter. During this Long Term Follow up Period, if a subject progresses or receives an intervening anti-cancer therapy, the subject will then enter the Survival Follow up Period.

Subjects who discontinue treatment due to clinical or radiological progression or are Lost to Follow up or Withdraw Consent will not enter Long Term Follow up, but will enter survival follow up as outlined below.

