4.1.5. Survival Follow-up Period

Following completion of the treatment and long term follow-up, as applicable, all subjects will be followed for survival. After that initial assessment of all study subjects, any surviving subjects will have their survival status assessed approximately every 3 months by either a telephone or in-person contact until study completion or termination by the Sponsor. With the exception of noting the first use of subsequent anti-cancer therapies, no other data (e.g., subsequent therapies, performance status etc.) beyond survival will be collected during these calls/visits.

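### Duration of response may be censored at an undefined follow-up call without tumor assessment, and counts deaths without time limit, so it can outlast the same subject's PFS

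*SAP*

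**What the plan says.** **DOR (SAP 9.1).** "DOR is defined as the time from first tumor assessment of CR, PR, or SD to the time of progressive disease or death", from any cause and with no time limit. For responders with neither event, "DOR will be censored on the last non-PD tumor assessment or follow-up call". The SAP does not define the call, does not say which of the two dates is used, and does not mention subsequent anti-cancer therapy.

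**Survival Follow-up (SAP 4.1.5).** Surviving subjects have their "survival status assessed approximately every 3 months by either a telephone or in-person contact". Apart from first use of a later anti-cancer therapy, "no other data (e.g., subsequent therapies, performance status etc.) beyond survival will be collected during these calls/visits". Protocol Table 13 agrees: its survival column has vital status and subsequent therapy, and no imaging.

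**Who enters it.** SAP 4.1.4 says that during long-term follow-up, "if a subject progresses or receives an intervening anti-cancer therapy, the subject will then enter the Survival Follow up Period". Protocol 12.1.4 has the same rule: "After documented disease progression or receipt of an intervening anti-cancer medication, patients will enter Survival Follow up". Subjects who withdraw consent from study treatment also go there directly (Protocol 5.3), as do those lost to follow-up according to SAP 4.1.4.

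**PFS (SAP 9.2).** Without a progression date, or with a death more than 126 days after the last tumor assessment, "the PFS time will be censored on the date of last tumor assessment", or at the last treatment date if there was no post-baseline assessment. No call is used.

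**Where progression is captured.** SAP 9.2 dates it at the end of treatment, when treatment ended for radiographic or clinical deterioration. SAP Appendix 1, item 5, also accepts the end-of-maintenance, follow-up and survival forms.

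**The concern.** A responder who leaves scan follow-up without progression is then known only to be alive. If a call in that period sets the DOR censoring date, the subject stays in the risk set as still responding, although nobody has looked at the tumor. Often the subject is on another drug by then. The open-ended death rule acts in the same way: a subject who dies long after the last scan has a DOR that runs to death.

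SAP 9.1 tabulates the Kaplan-Meier median DOR by treatment and subgroup. That median may then mix duration of response with survival on later treatment, with a likely upward bias. One subject's DOR could also exceed their PFS, although DOR starts later. That cannot happen if both describe the same disease course under the same stopping rule.

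**Working it through.** **Figures in the plan.** The documents give no median, event count or sample size for DOR, so there is none to reproduce. The one related figure checks: 126 days / 63 days (the 9-week scan interval) = 2 intervals, as SAP 9.2 says.

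**The two stopping rules side by side**

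| | DOR (SAP 9.1) | PFS (SAP 9.2) |
|---|---|---|
| Censoring date | last non-PD assessment or follow-up call | last tumor assessment (last treatment date if none post-baseline) |
| Late deaths | counted at any time | not counted beyond 126 days after the last assessment |
| Subsequent therapy | no rule | no rule |

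**One illustrative subject (assumed).** Response at the week 12 scan, last scan at week 21, treatment ended for a reason other than deterioration, new therapy at month 5, alive at a call at month 24. The conversion is the SAP's own 30.4375 days per month (SAP 8.3).

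- Start of response: 84 / 30.4375 = 2.76 months.
- Last scan: 147 / 30.4375 = 4.83 months.
- DOR censored at the last scan: 4.83 − 2.76 = 2.07 months.
- DOR censored at the call: 24 − 2.76 = 21.24 months.
- PFS: censored at 4.83 months.

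If the subject had instead died at month 24, the gap from the last scan would be 24 × 30.4375 − 147 = 583.5 days, beyond 126. PFS would still be censored at 4.83 months, but DOR would be an event at 21.24 months. Deleting the call alone is therefore not enough.

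**Dependence on follow-up length (assumed).** Scans at weeks 12 and 21, new therapy at week 23, then calls every 13 weeks. Censoring at the last scan gives 21 − 12 = 9 weeks. The last call within 1, 2 or 3 years falls at week 49, 101 or 153, which gives 37, 89 or 141 weeks.

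**Effect on the median (simulation, all inputs assumed).** There were 6,000 responders per scenario with 24 months of follow-up. Time to progression was exponential and detected at the next 63-day scan. Switching therapy was independent of progression, survival after the switch was exponential, and calls came every 3 months. Under the rule as written, a switcher has an event at death or is censored at the last call. The comparator censors at the last scan before the switch. Median DOR in months:

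| True median time to progression | Switch before progression | Censored at last scan | As written, median survival after switch 9 mo | As written, 15 mo |
|---|---|---|---|---|
| 3 | 10% | 4.1 | 4.1 | 4.1 |
| 3 | 30% | 4.1 | 4.1 | 4.1 |
| 3 | 50% | 4.1 | 5.6 | 6.2 |
| 6 | 10% | 6.2 | 6.2 | 7.5 |
| 6 | 30% | 6.2 | 7.6 | 8.3 |
| 6 | 50% | 6.2 | 8.3 | 8.6 |

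The shift runs from 0 to 8.6 − 6.2 = 2.4 months. Scan-detected progression falls on a grid of 63 / 30.4375 = 2.07 months, so a zero shift means only that the median stays at the same scan. The comparator does not count deaths within 126 days of the last scan, so it only approximates the result of the proposed fix.

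**The case against.** **The call is undefined.** It might not be the survival call. The protocol also has a safety contact within 28 days of the last dose (Protocol 12.1.5). This stands as a caution: the survival call is the natural reading but not a certain one. On either reading no tumor assessment is specified for the contact, and two programmers could choose different dates.

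**Progression can be recorded without a scan.** In this SAP progression is the investigator's judgement of clinical or radiological deterioration, and Appendix 1, item 5, lists the survival form as a source. A contact with no deterioration reported could then be a defensible censoring point. But SAP 4.1.5 says that these contacts collect survival and first later therapy only, and SAP 9.2 ties the progression date to the end of treatment. The SAP conflicts with itself here. If 9.2 governs, even a responder who completes treatment and progresses later may have no progression date.

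**Not all of the excess is time on another drug.** A reader might infer that every such call follows a new therapy. The documents do not support that: withdrawal of consent, and in the SAP loss to follow-up, also lead to Survival Follow-up. For those subjects the problem is unassessed time.

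**The factor of about ten.** A reader might apply 21.24 / 2.07 to every responder who switches. It belongs to one invented subject; the weekly illustration gives 37 / 9 to 141 / 9, about 4 to 16, from the assumed follow-up alone. These are also censoring times, which lengthen time at risk and move the median only if enough responders are affected.

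**Censoring at new therapy.** It is tempting to call this the correction. It is an estimand choice: SAP 9.2 has no such rule for PFS, and applying it to DOR alone would create a new mismatch.

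**Conclusion.** The concern holds as a defect in the stopping rule for DOR. As written, SAP 9.1 permits censoring at a contact with no tumor assessment and sets no limit on late deaths. DOR can then run past the same subject's PFS, and the Kaplan-Meier median may be biased upward.

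The size cannot be fixed from the documents, because they do not give the number of responders who leave scan follow-up without progression. The range of 0 to about 2.4 months rests on the assumed progression times, switching rates and survival after switching, and on reading the call as the survival call.

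A reader might infer that the trial's main efficacy result is affected. It is not: SAP Table 2 lists DOR among the exploratory endpoints, and the disease control rate does not use this rule.

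**What to change.** 1. In SAP 9.1, delete the follow-up call and count death as a DOR event only within 126 days of the last tumor assessment, as SAP 9.2 does for PFS. Suggested wording: *Responders with no progression, and no death within 126 days of the last tumor assessment, are censored at the last evaluable non-PD tumor assessment.* In the illustration this gives a DOR of 2.07 months beside a PFS of 4.83 months.
2. Reconcile SAP 4.1.5, SAP 9.2 and Appendix 1, item 5, on which forms can record progression and which date is used, and apply the answer to both endpoints.
3. If censoring at subsequent anti-cancer therapy is wanted, apply it to both DOR and PFS, or report it as a sensitivity analysis. The date is already in the disposition listing (SAP 8.1).

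The cost is a few SAP sentences and a small programming change, with no new data. The downside for the sponsor is a possibly shorter, less favourable median DOR.
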